# **Project Proposal**

You must upload a scientific proposal (not an IRB Protocol) in order for the project to be approved. This proposal should include scientific descriptions of all activities that will be approved under this project (i.e., fellowships).

If you do not have a full proposal you may upload a Letter Of Intent instead. Please see the Guidelines for LOI Format.

Uploaded Project Proposal or Scientific (not IRB)

Protocol\*: Proposal\_60667.pdf

### Project Summary/Abstract

Please limit the following sections to a total of 150 words each.

## Objectives\*

The overall goal of this research program is to improve mental health care in Veterans by increasing the availability of mental health care that is non-stigmatizing and easily available to Veterans who have untreated mental health problems, but choose not to seek or accept face-to-face VHA mental health care services. The specific aims of this pilot study are preparatory to a large-scale RCT to test the effects of Moving Forward (MF) with and without peer support (PS) on two populations of Veterans who have untreated mental health problems.

Aim 1: Test feasibility and acceptability of recruitment and data collection strategies to study MF + PS in two populations of Veterans with unmet mental health needs.

Aim 2: Obtain preliminary efficacy results on the impact of MF and MF+PS on problem-solving skills and psychological health in Veterans with unmet mental health needs.

### **Research Plan and Methods\***

This pilot study aims to investigate the feasibility and acceptability of methods to study the impact of the online problem-solving training, Moving Forward, with and without peer support, in Veterans with untreated mental health problems. We will study 60 VHA primary care patients who are referred for mental health treatment but decline or do not attend a mental health intake session and 60 Veterans living in the community who have untreated mental health problems. We will adapt an existing guide for peer support for an online mental health program for use with MF, train a PS to support use of MF, and monitor fidelity to the guide throughout the study. All who agree to enroll will be referred to a study website, where they will be screened, provide informed consent, and complete baseline assessments of problem-solving skills and psychological health, which will include measures of quality of life, depression, anxiety, and PTSD. Participants will then be randomized to one of 3 conditions: a no-treatment control group, MF, or MF+PS. Participants in the two active intervention groups will be asked to complete the 8 MF modules over 4 weeks and spend an additional 4 weeks using MF. Mid-point and end-of-program assessments of problem-solving and psychological health will be completed, and use of the MF intervention will be objectively measured through the web site. Several indicators of feasibility and acceptability will be assessed to inform a large-scale RCT. User satisfaction, qualitative data on barriers and facilitators to use of MF and PS, and perceptions of usefulness of MF and PS will also be assessed. If results are encouraging, they will be disseminated and a Merit grant application for a large-scale RCT will be developed.

### Clinical Relevance to the VA Mission\*

The population of Veterans with mental health (MH) care needs is large and is projected to continue growing for another 15 years, but many of these Veterans go without care due to stigma, logistical challenges, and a high value on self-sufficiency. VHA has developed online, evidence-based, interactive programs aimed at fostering MH that may be more acceptable than psychotherapy and has established a peer support program, but these programs have not been the focus of rigorous research. If an online program can improve MH and

peer support can boost the program's use and effectiveness, peer support staff could be trained to coach a range of already available programs and deliver MH care to Veterans who decline other MH care. Results of this pilot study of feasibility and acceptability would inform a larger study of the impact on problem-solving and psychological health of a non-stigmatizing, online program - with and without peer support. If effective, peer supported online programs would improve the quality of care to Veterans with unmet MH needs.

### **Data Collection And Analysis**

#### Yes

If Yes, please describe your plans for statistical analysis:

To address Aim 1, To accomplish Aim 1, we will collect data on the study measures and on these indicators:

# enrolled per month; % of eligible who enroll

% of PS sessions achieving fidelity after training completion

% in control group who use MF during 8 weeks of study

% completing mid-way and post-study measures

Time using the online program, working with peer supporter

% of enrolled participants reporting problems using MF online

% of enrolled participants with complete data

% in MF and MF + PS who complete 6+ modules

% of those in MF + PS who have 4+ sessions with PS

% in MF and MF + PS who rate program as helpful

% satisfied/very satisfied with care, amount/type of PS contact

Post-training survey about barriers and facilitators to MF use, measures, usefulness of working with PSS, specific impact of PS on use of MF, and mpact on problem-solving skills.

Are target variable SDs in appropriate range for intervention?

We will also interview 40-50 Veterans and the Peer Support Specialist about barriers and facilitators to MF use, the study PS processes, and suggestions for improvements of the PS Guide for MF. We will also ask the PS about characteristics of Veterans who seemed to benefit the most or the least from MF and PS, modules of MF that were most and least difficult to support, and aspects of MF that the PS found confusing or unclear.

To address Aim 2, we will conduct analyses to determine whether a very broad confidence interval for an effect size (e.g., 90%) of MF + PS on problem-solving includes a small effect. MF alone may not have an impact due to lack of MF use and engagement, but we expect PS to increase MF use and engagement and MF + PS to improve psychological health. Multilevel Modeling will be used to test Condition X Time effects on problem-solving, engagement with the MF course, and psychological health. This approach has the advantages of a) permitting missing data, b) modeling within- and between-person differences in change across time, and c) inclusion of potential moderating variables in the model (e.g. usage). Power for a Condition X Time interaction for symptoms was estimated using GLIMMPSE 2.2.3 (64) to be .58, with on N =120, alpha = .05, 3 assessments, and pre- to post-intervention standardized effect size estimates of .80, .47, and 0 for the MF + PS, MF alone, and control conditions, respectively. Calculations were based on baseline mean and SD estimates from a study of VHA patients with depression symptoms (65) and effect size estimates from Greene et al. (34). A correlation will be calculated between participant age and positive impacts for problem-solving and for psychological health. We

expect a small effect (r = -.1 to -.2). A large effect (r = -.5) would indicate that older Veterans are less likely to benefit from MF. Power to detect a large effect with N = 80 and alpha = .05 will be .99 (66).

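### The Aim 1 indicator for problems using Moving Forward is taken over all enrolled participants, so it counts no-treatment controls who are not asked to use the program

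*Combined protocol and SAP*

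**What the plan says.** The Aim 1 indicator list, under Data Collection And Analysis, includes the percentage "of enrolled participants reporting problems using MF online". It names no arm and does not limit the count to people who used MF.

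Research Plan and Methods sets out the design: "Participants will then be randomized to one of 3 conditions: a no-treatment control group, MF, or MF+PS". It then says who is to use the program: "Participants in the two active intervention groups will be asked to complete the 8 MF modules over 4 weeks".

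Other lines in the same list choose their denominators with more care:

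- Module completion is the percentage "in MF and MF + PS who complete 6+ modules".
- Helpfulness is the percentage "in MF and MF + PS who rate program as helpful".
- Use of MF outside the assigned arms has its own line, the percentage "in control group who use MF during 8 weeks of study".
- Completeness of data is the percentage "of enrolled participants with complete data". All enrolled is the natural denominator there, because every arm is assessed.

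**The concern.** A usability rate should describe people who were given the program. Here the denominator also holds an arm that is not asked to use it. A control who never opens MF has no problem to report, yet counts as a person without one.

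Some controls may find MF themselves. Clinical Relevance to the VA Mission speaks of "a range of already available programs", and the list tracks control use. The single percentage would therefore mix three groups: Veterans assigned MF, controls who start it unprompted, and controls with no exposure.

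The pilot is meant to inform a large trial, and difficulty using an online program bears directly on acceptability. If the dilution runs downward, it runs in the reassuring direction. The Aim 2 text already expects that MF alone may have no effect because Veterans do not use it or engage with it. An understated problem rate would hide one possible reason.

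**Working it through.** The documents give no expected value or target for this indicator, so there is no stated figure to reproduce. What can be checked is how the reported percentage relates to the rate among those assigned MF.

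**Inputs**

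- Total enrolled: 120, from 60 VHA patients and 60 community Veterans (Research Plan and Methods).
- Arm sizes: not stated. I assume 40 each. This fits the N = 80 in the age-correlation power statement if that means the two active arms, but the text does not say so.
- Problem rate and share using MF in each arm: not given. Ranges are shown.

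**Step 1: direction.** Let A be the share of assigned participants (MF or MF + PS) who report a problem, and C the share of controls who do. The indicator as written is

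R = (80A + 40C)/120 = 2A/3 + C/3, so R − A = (C − A)/3.

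R lies below A exactly when C is below A.

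**Step 2: size.** Suppose only users of MF can report a problem, at the same rate p in every arm. Let a be the share of assigned participants who use MF and c the share of controls who do. Then A = ap, C = cp, and

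R/A = 2/3 + c/(3a).

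| Control use c | R/A, all assigned use MF (a = 1) | R/A, half of assigned use MF (a = 0.5) |
|---|---|---|
| 0 | 0.667 | 0.667 |
| 0.25 | 0.667 + 0.25/3 = 0.750 | 0.667 + 0.25/1.5 = 0.833 |
| 0.50 | 0.667 + 0.50/3 = 0.833 | 0.667 + 0.50/1.5 = 1.000 |

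The factor reaches 1 when c = a, that is, when controls use MF as often as assigned participants do.

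**Step 3: in percentages.** Take A = 30% for illustration. For c = 0, 0.25 and 0.50 the indicator reads 20.0%, 22.5% and 25.0% if a = 1, and 20.0%, 25.0% and 30.0% if a = 0.5. In reverse, a reported 20% divided by the factor gives an assigned-arm rate of 30.0%, 26.7% or 24.0% if a = 1, and 30.0%, 24.0% or 20.0% if a = 0.5.

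**Step 4: unequal problem rates.** Let a = 1 and p = 30%, but let control users report problems at 45%. At c = 0.25, R = (2/3 × 30%) + (1/3 × 0.25 × 45%) = 20% + 3.75% = 23.8%. The direction reverses once c exceeds 0.30/0.45 = 0.67.

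**Step 5: other allocations.** With no control use, the factor is simply the share of enrolled participants assigned to MF: 96/120 = 0.80 for a 24/48/48 split (control, MF, MF + PS), and 60/120 = 0.50 for 60/30/30.

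**The case against.** The strongest reply is that the list is shorthand in an application form whose scientific proposal was uploaded separately. The neighbouring lines suggest that the active arms were meant here too, and enrolled may be loose wording. That is plausible, but nothing in the available text says so, and the words as they stand give a definite denominator. If they are loose, the same one-line correction settles the matter.

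A second reply concerns consequence. The indicator feeds no test, and arm is known, so the rate can be recomputed. Usability is also covered by a post-training survey, interviews with 40 to 50 Veterans, time spent on the program and website use data. All of this stands and keeps the point minor.

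A third concerns size and direction. A reader might infer that the figure is always too low, and that it matches the assigned-arm rate only if every control uses MF. Neither follows. The match occurs when controls use MF as often as assigned participants, and the plan itself anticipates incomplete use in the MF-alone arm. The direction can reverse if control users have more trouble and are numerous. Only the two-thirds figure at zero control use is free of assumptions about use and problem rates, and it still needs equal arms.

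**Conclusion.** The point holds as a minor one. The stated denominator includes an arm that is not asked to use MF, which is out of line with the two comparable indicators in the list. The result understates the problem rate among assigned Veterans whenever problems are less common among controls than among those assigned. With 40 per arm it is two thirds of that rate if no controls use MF, and comes closer to it as control use approaches use in the assigned arms. Equal arms, and an equal problem rate among users, are assumptions.

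Two further inferences are not supported. One is that the error would change a decision about the larger trial: no threshold or go/no-go rule is attached to this indicator. The other is that the share of eligible Veterans who enroll has a similar denominator fault: the form does not define who counts as eligible, so that cannot be shown.

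**What to change.** Define the indicator as the percentage of participants assigned to MF or MF + PS who report problems using it. Report problems among controls who used MF in a separate line, next to the existing indicator of control use.

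The assigned-arm rate will still include Veterans who never open the program. If a rate among users is also wanted, add a second figure for those who opened MF, taken from the website use data.

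The cost is a change of wording. Arm is already recorded, use of MF is already to be measured through the website, and no new data are needed. Settling the denominator now avoids choosing it after the results are seen.

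### The Aim 2 Condition X Time model does not say how baseline enters; fixing one common baseline mean across the randomised arms would gain precision at no cost

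*Combined protocol and SAP*

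**What the plan says.** The Aim 2 text under Data Collection And Analysis states that "Multilevel Modeling will be used to test Condition X Time effects on problem-solving, engagement with the MF course, and psychological health". The power statement there is for the same interaction on symptoms: "Power for a Condition X Time interaction for symptoms was estimated using GLIMMPSE 2.2.3 (64) to be .58". The inputs listed are 120 participants, a 5% alpha and three assessments. The effects assumed are "pre- to post-intervention standardized effect size estimates of .80, .47, and 0 for the MF + PS, MF alone, and control conditions, respectively". On scale, it says only that "Calculations were based on baseline mean and SD estimates from a study of VHA patients with depression symptoms".

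Research Plan and Methods gives the order of events. Baseline measures of problem-solving and psychological health are completed first, and "Participants will then be randomized to one of 3 conditions". After that, "Mid-point and end-of-program assessments of problem-solving and psychological health will be completed". Only two assessments follow randomisation, so baseline must be one of the three.

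The plan does not say whether baseline means are free in each arm, held equal, or used as a covariate. It gives no correlation between assessments, numeric SD, covariance structure, mid-point effect, allocation ratio or dropout rate.

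**The concern.** In the usual Condition X Time model, baseline is an outcome like any other and each arm has its own baseline mean. The interaction then compares arms on raw change. Including baseline as a repeated outcome in this way does not give the precision of adjusting for it. Randomisation makes the three true baseline means equal, so estimating them separately uses up information for nothing.

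At stake is precision. Aim 2 turns on a 90% confidence interval for the effect of MF + PS on problem-solving and on whether it includes a small effect, so the interval's width decides how informative the answer is. The power quoted for the symptom interaction is only .58. In a pilot of 120 people meant to inform a larger trial, precision that needs no extra participants is worth having.

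**Working it through.** **Inputs from the documents.** N = 120, three arms, alpha .05, three assessments, pre-to-post effects .80, .47 and 0, stated power .58.

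**Assumptions.** 40 per arm (consistent with the N = 80 used for the age correlation, if that is the two active arms), equal SDs at all visits, no dropout, compound symmetry with correlation r, and a mid-point effect half the final one. The formulas are large-sample.

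**Step 1: the plan's own figure.** The mean of the three effects is 1.27/3 = .4233. The sum of squared deviations is .64 + .2209 − 3 × .4233² = .3233. With unit SD and a free baseline in each arm, the noncentrality of the 4-df interaction test is 40 × .3233 × .5/(1−r) = 6.465/(1−r). The factor .5 comes from the half-size mid-point effect. Power is .67 at r = .3 and .83 at r = .5. Power of .58 needs a noncentrality of 7.77, hence r = 1 − 6.465/7.77 = .17. A 2-df test of pre-to-post change alone gives .77 at r = .3 and .90 at r = .5, and would need r = −.06 to give .58. So .58 can be neither confirmed nor refuted from the stated inputs.

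**Step 2: variance of one contrast.** For a difference between two arms of n at one follow-up visit, with SD σ:

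- free baseline (change score): (2/n) × 2σ²(1−r)
- common baseline mean: (2/n) × σ²(1−r²)
- ratio: (1−r²)/[2(1−r)] = (1+r)/2

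The ratio is below 1 for every r below 1.

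**Step 3: omnibus test, starting from .58.** Under the assumptions above, the common-baseline noncentrality is the free-baseline value times 2.5 − 4.5r/(1+2r). At r = .5 this is 2.5 − 2.25/2 = 1.375. Holding the free-baseline noncentrality at 7.77 (that is, rescaling the SD so that the planned test has power .58 at each r) gives:

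| Assumed r | Variance ratio, one contrast | Saving | Noncentrality multiplier | Omnibus power, free to common |
|---|---|---|---|---|
| .3 | .65 | 35% | 1.656 | .58 to .82 |
| .5 | .75 | 25% | 1.375 | .58 to .74 |
| .7 | .85 | 15% | 1.188 | .58 to .67 |
| .8 | .90 | 10% | 1.115 | .58 to .63 |
| .9 | .95 | 5% | 1.054 | .58 to .61 |

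**Step 4: the 90% interval.** For MF + PS against control at end of program, with r = .5, unit SD and 40 per arm:

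- free baseline: 1.645 × √[(2/40) × 2 × .5] = 1.645 × .224 = .37 SD
- common baseline: 1.645 × √[(2/40) × .75] = 1.645 × .194 = .32 SD

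**Step 5: unequal SDs.** With baseline SD σ0 and follow-up SD σ1, the free-baseline variance exceeds the common-baseline variance by (2/n)(σ0 − rσ1)². This is never negative, so the constraint does not lose precision, but the gain can be small. At r = .5 with σ1 = 1.48σ0 the ratio is (2.190 × .75)/(1 + 2.190 − 1.48) = 1.643/1.710 = .96, a saving of 4%.

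**The case against.** The strongest reply is that the plan never says baseline is free in each arm. A model with no condition effect at baseline also has Condition X Time terms, so the efficient analysis may be what was meant. This stands as a limit on the wording: the free baseline is the default reading, supported by the three assessments and the pre-to-post effect sizes, but it is inferred. The remedy is the same either way, because the plan should say which model it uses.

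The second reply is that the size of the gain is unknown. That also stands. A reader who solves for the r that yields .58 gets .17 and might infer that power would rise from .58 to .88. The documents do not support this as the plan's gain: r = .17 appears nowhere, and it follows only from assuming unit SD, compound symmetry, 40 per arm and a half-size mid-point effect. Other inputs also give .58 with a smaller gain.

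A reader might also infer that chance baseline differences pass in full into the change contrast. With equal SDs, a baseline difference d shifts the expected difference in change by −(1−r)d, so only part carries over, with the sign reversed.

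The third reply is that this is a pilot seeking preliminary efficacy results with a deliberately broad interval, and that the conventional analysis is unbiased with correct type I error. This is true and sets the weight of the point. It does not remove it, since the better model uses the same data and participants.

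Finally, the quoted sentence also covers engagement. Use of the online program is recorded by the website, and no baseline measure of it is described, so the argument does not extend to that outcome.

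**Conclusion.** The point holds as a free efficiency improvement for problem-solving and the psychological-health measures. How baseline enters the model is unspecified. Under the usual specification the interaction compares raw change, and a common baseline mean, justified by randomisation after baseline, cuts the variance of each baseline-to-follow-up contrast to (1+r)/2 when SDs are equal. The saving runs from 35% at r = .3 to 5% at r = .9: material at moderate correlations and slight at high ones. Power starting from .58 would be about .82 to .61 over the same range, given the Step 3 assumptions. These sizes rest on assumed values of r, because the documents give none. It would be wrong to conclude that the planned analysis is biased or invalid, or that the .58 has been shown to be miscalculated.

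**What to change.** For problem-solving and each psychological-health measure, specify a multilevel model with categorical visit, one common baseline mean for all three arms, and condition effects at mid-point and end of program. An alternative is to model the two follow-up scores with the baseline score as a covariate and a separate baseline slope at each visit. The two can differ when follow-up is missing, so the plan should name one. Report the end-of-program contrasts and the 90% interval from that model. Restate the power for it, giving the assumed correlation, SDs, covariance structure and mid-point effect. Treat engagement separately, as it has no described baseline.

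The cost is a sentence or two in the analysis plan and a re-run of the power calculation. No new data or participants are needed, and type I error is preserved because baseline precedes randomisation.

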# **Medical Subject Heading Terms (Keywords)**

List three or more unique MeSH Keywords\* to describe your project.

At least three must exactly match terms found in the MeSH terms browser.

Check your text for MeSH Terms.

Keywords will be an important aspect to finding your project in database searches, so be as specific as possible. Please check your spelling. Entries will be checked when you save the page, and those without a unique MeSH ID will be flagged. Click on the flag to view the MeSH database entry for that term in order to refine your entry.

Coaching	Problem Solving
Veterans	Mental Health
Stress Disorders, Post-Traumatic	Internet

### **PI Link**

This is a voluntary opportunity for you to find and collaborate with your research colleagues at the VA based on shared research interests and techniques.

Read more about PI Link.

About PI Link Reports.

This information is **not required** for review or approval of your projects.

Please select at least one item in each category that applies to this project.

[n/a] I decline. I do not want to be considered as a potential collaborator or PI; nor as a potential beneficiary for additional resources.

